4.2.3.3 Boys and girls with reproductive potential – contraception and pregnancy prevention

Patients who are not of reproductive potential (i.e. pre-pubertal) do not need to use contraception to be eligible for the trial.

All other patients are considered to have childbearing potential (had 1st menarche or 1st ejaculation) and must use adequate contraception throughout the trial if sexually active (from screening until 28 days after last dose of trial medication). Highly effective methods of birth control per ICH M3 (R2) are methods that result in a low failure rate of less than 1% per year when used consistently and correctly ([R09-1400](#)). These include hormonal contraception associated with inhibition of ovulation, IUD, intrauterine hormone-releasing system, bilateral tubal occlusion, partner vasectomy (if vasectomized partner is sole sexual partner) ([R16-0373](#)). When using hormonal contraceptives, or with partners using hormonal contraceptives, patients must also be using an additional approved barrier method of contraception, i.e. condom or occlusive cap with spermicide, or vasectomised partner.

A method of contraception which is not considered highly effective (> 1% failure rate) is the double barrier method. Double barrier method of contraception is defined as two barrier methods used simultaneously each time the patient has intercourse. Use of male and female condom together, partner vasectomy (if different sexual partners), natural "rhythm" and spermicidal jelly/cream are not acceptable methods of contraception.

Female patient who become pregnant while participating in the study must discontinue study medication immediately. The pregnancy must be reported following procedures detailed in [Section 5.2.2.3](#).

4.3 TREATMENT COMPLIANCE

The appropriate number of afatinib tablets/ afatinib liquid formulation for 4-weeks of treatment will be provided to the patients to be self-administered at home. An appropriate number of syringes will be co-supplied with afatinib oral liquid formulation. The patient will be requested to maintain a medication diary of each dose of medication. The medication diary

Proprietary confidential information.

© 2017 Boehringer Ingelheim International GmbH or one or more of its affiliated companies. All rights reserved.

This document may not - in full or in part - be passed on, reproduced, published or otherwise used without prior written permission.

will be returned to clinic staff at the end of each course. During the first treatment course, compliance may also be verified by pharmacokinetic assessment.

Patients will be asked to bring the remaining trial medication at the end of each 4-week period to the investigational site for a compliance check. The remaining film-coated tablets will be counted by the investigator/site staff and the remaining volume of afatinib oral liquid formulation will be estimated as well (for details refer to ISF) and recorded at the investigational site. Discrepancies between the number of tablets/amount of liquid formulation remaining and the calculated amount of medication the patients should have taken must be documented and explained. An early compliance check at course 1 day 8 will be done by the investigator/site for ensuring that the medication is being taken correctly. At the end of each 4-week period, any remaining medication will be collected. If the patient is eligible for further treatment, new bottle(s) of study medication must be dispensed.

The investigator and/or the sponsor should discuss patient's withdrawal from the study in the event of serious and persistent non-compliance which jeopardizes the patient's safety or renders study results for this patient unacceptable. Patients who do not attend a minimum of 75% of scheduled study visits, unless due to exceptional circumstances, should be discussed with the BI trial monitor and be evaluated for compliance. For afatinib, a maximum of 25% of the dispensed afatinib doses may be missed for other reasons than drug-related AEs. For details, see [section 7.3](#). Patients who miss afatinib treatment more frequently are considered non-compliant.

During the first course of the dose finding part, patients should not miss more than 25% of afatinib doses (regardless of the reason of missed doses) to render patients evaluable for MTD. For details, see [section 7.3](#).

5. VARIABLES AND THEIR ASSESSMENT

For details on time points of evaluation and specific assessments, refer to the following Sections [5.1](#), [5.2](#) and [5.5.1](#).

The endpoints are categorised as follows and explained in more detail in the sections below:

Primary Endpoint

- In dose finding part
 - o DLT measured during the first course of treatment
 - o Pharmacokinetics ($AUC_{\tau,ss}$, $C_{max,ss}$)
- In MTD expansion cohorts/Phase II part
 - o Objective Response by investigator assessment according to the institutional response evaluation criteria for the given tumour type, assessed every 8 weeks until progression of disease.

Secondary Endpoints

- In dose finding part
 - o Objective Response by investigator assessment according to the institutional response evaluation criteria for the given tumour type, assessed every 8 weeks until progression of disease.
 - o Pharmacokinetics (AUC_{0-24} , C_{max} , $t_{max(ss)}$ and accumulation (or effective) half-life)
- In MTD expansion cohorts/Phase II part
 - o Progression free survival (PFS)
 - o Duration of objective response (DoR)
 - o Pharmacokinetics ($AUC_{\tau(ss)}$, $C_{max(ss)}$, $t_{max(ss)}$ and accumulation (or effective) half-life)

Proprietary confidential information.

© 2017 Boehringer Ingelheim International GmbH or one or more of its affiliated companies. All rights reserved.

This document may not - in full or in part - be passed on, reproduced, published or otherwise used without prior written permission.

5.1 EFFICACY - CLINICAL PHARMACOLOGY

5.1.1 Endpoint(s) of efficacy

5.1.1.1 Primary endpoint

For the dose finding part, a primary endpoint of efficacy is not applicable. The primary endpoint for safety is described in [Section 5.2.1](#).

In the MTD expansion cohorts/Phase II part, the primary endpoint will be objective response by investigator assessment according to the institutional response evaluation criteria for the given tumour type, assessed every 8 weeks until progression of disease.

5.1.1.2 Secondary endpoints

In the dose finding part of this trial, the objective tumour response (OR) assessed by investigator assessment according to the institutional response evaluation criteria for the given tumour type will represent a secondary endpoint.

In the MTD expansion cohorts/Phase II part, progression free survival (PFS) and duration of objective response (DoR) will be secondary endpoints for efficacy. PFS is defined as the duration of time from the date of first treatment until the date of the first documented progression or death due to any cause. If a patient has not had an event, PFS will be censored at the date of last adequate tumour assessment. Duration of overall objective response (DoR) is defined only for those patients with a response (CR or PR) as the interval between the date of randomization and the earliest date of disease progression.

5.1.2 Assessment of efficacy

Response and progression will be evaluated in this study by investigator assessment according to the institutional response evaluation criteria for the given tumour type.

Each tumour type should be assessed using appropriate techniques. The method used at baseline must be continuously used throughout all consecutive tumour assessments.

In addition, all image data will be sent to a central imaging unit for digitization, quality control and archiving. If deemed necessary, a retrospective independent review of radiographic images may be performed. All procedures will be done according to the specifications provided in the investigator site file.

5.2 SAFETY

5.2.1 Endpoint(s) of safety

Primary endpoint: DLT

Proprietary confidential information.

© 2017 Boehringer Ingelheim International GmbH or one or more of its affiliated companies. All rights reserved.

This document may not - in full or in part - be passed on, reproduced, published or otherwise used without prior written permission.

The primary objective of the dose finding part is to determine the MTD as defined by patients with DLT in a paediatric population. It will be reported as primary endpoint of safety in this part of the trial.

For the purpose of dose escalation, patients with DLT events that occur during the first treatment course will be considered. Decisions on dose escalation/dose de-escalation will be made only after discussion between the sponsor and the investigators/steering committee, and in consideration of all the available toxicity and pharmacokinetic data. For details on the determination of MTD and definition of DLT, please refer to sections [4.1.4.1](#) and [7.3.1](#).

Once the MTD will be obtained, the MTD expansion cohorts/Phase II part will allow further collection of safety data and efficacy data. DLT will be monitored throughout the whole trial and all safety data will be collected in order to confirm the safety of the recommended Phase II dose.

Other safety endpoints will include:

- The overall incidence and CTCAE grade of adverse events, as well as relatedness of adverse events to treatment
- Events leading to dose reduction
- Events leading to permanent treatment discontinuation
- AESI
- Causes of death

The safety of afatinib will be assessed by a descriptive analysis of incidence and intensity of adverse events graded according to US NCI CTCAE Version 3.0 ([R04-0474](#)).

5.2.2 Assessment of adverse events

Safety assessments will consist of monitoring and recording all adverse events (AEs) and serious adverse events (SAEs) and include periodic physical examinations, measurement of vital signs, assessment of performance status, monitoring of laboratory tests (i.e. haematology, chemistry, coagulation, urine analysis), assessment of cardiac function with periodic ECGs and echocardiograms, pregnancy test(s) as outlined in the Schedule of Procedures/Assessments ([Section 6.2.1](#)).

If the investigator becomes aware of an SAE or AESI after the FU visit (28-30 days after the last dose of study drug), it should be reported by the investigator to the sponsor if considered relevant by the investigator.

A diagram of the Adverse Event/Serious Adverse Event reporting requirements is provided in [Table 5.2.2.2:1](#)

5.2.2.1 Definitions of adverse events

Adverse event

An adverse event (AE) is defined as any untoward medical occurrence, including an exacerbation of a pre-existing condition, in a patient in a clinical investigation who received a

Proprietary confidential information.

© 2017 Boehringer Ingelheim International GmbH or one or more of its affiliated companies. All rights reserved.

This document may not - in full or in part - be passed on, reproduced, published or otherwise used without prior written permission.

pharmaceutical product. The event does not necessarily have to have a causal relationship with this treatment.

An AE can therefore be any unfavourable and unintended sign (including an abnormal laboratory finding), symptom, or disease temporally associated with the use of a medicinal product, whether or not considered related to the medicinal product.

Serious adverse event

A serious adverse event (SAE) is defined as any AE which results in death, is immediately life-threatening, results in persistent or significant disability / incapacity, requires or prolongs patient hospitalisation, is a congenital anomaly / birth defect, or is to be deemed serious for any other reason if it is an important medical event when based upon appropriate medical judgement which may jeopardise the patient and may require medical or surgical intervention to prevent one of the other outcomes listed in the above definitions.

Cancers with new histology are always considered serious.

The following hospitalizations are not considered to be serious adverse events (SAEs) because there is no “adverse event” (i.e., there is no untoward medical occurrence) associated with the hospitalization:

- Hospitalizations for respite care
- Planned hospitalizations required by the protocol (including anaesthesia for imaging exams)
- Hospitalization planned prior to informed consent (where the condition requiring the hospitalization has not changed post study drug administration)
- Hospitalization for administration of study drug

Intensity of adverse event

The intensity of the AE should be judged based on the following:

- The intensity of adverse events should be classified and recorded according to the Common Terminology Criteria for Adverse Events (CTCAE) v3.0 in the (e)CRF.

Causal relationship of adverse event

Medical judgment should be used to determine the relationship, considering all relevant factors, including pattern of reaction, temporal relationship, de-challenge or re-challenge, confounding factors such as concomitant medication, concomitant diseases and relevant history. Assessment of causal relationship should be recorded in the case report forms.

Yes: There is a reasonable causal relationship between the investigational product administered and the AE.

No: There is no reasonable causal relationship between the investigational product administered and the AE.

Proprietary confidential information.

© 2017 Boehringer Ingelheim International GmbH or one or more of its affiliated companies. All rights reserved.

This document may not - in full or in part - be passed on, reproduced, published or otherwise used without prior written permission.

The reason for the decision on causal relationship needs to be provided in the eCRF and on the SAE form (if applicable).

Worsening of the underlying disease or other pre-existing conditions

Worsening of pre-existing conditions other than underlying disease will be recorded as an (S)AE in the (e)CRF.

Exemptions to SAE Reporting

Disease Progression is a study endpoint for analysis of efficacy. Disease progression is exempted from reporting as a (S)AE. Progression of the patient's underlying malignancy, including death due to progression of the underlying malignancy, will be recorded in the appropriate pages of the (e)CRF as part of efficacy data collection.

Examples of exempted events of PD are:

- Progression of underlying malignancy (Progressive disease PD): if PD is clearly consistent with the suspected progression of the underlying malignancy as defined by the respective response criteria.
- Hospitalization/Procedures due solely to the progression of underlying malignancy (PD)
- Clinical symptoms and/or signs of progression (with or without confirmation by objective criteria e.g. imaging, clinical measurement): if the symptom can exclusively be determined to be due to the progression of the underlying malignancy and does meet the expected pattern of progression for the disease under study.

However, when there is evidence suggesting a causal relationship between the drug and the progression of the underlying disease, the event must be reported as (S)AE in the eCRF and on the SAE Form.

Changes in vital signs, ECG, physical examination, and laboratory test results

Changes in vital signs, ECG, physical examination and laboratory test results will be recorded as an (S)AE in the (e)CRF, if they are judged clinically relevant by the investigator.

Adverse Events of special interest (AESIs)

Protocol-specified AESIs

The following are considered as Protocol-specified AESIs:

- *Hepatic injury* defined by the following alterations of liver parameters:
 1. For patients with normal liver function (ALT, AST and bilirubin within normal limits) at baseline an elevation of AST and/or ALT ≥ 3 fold ULN combined with an elevation of bilirubin ≥ 2 fold ULN measured in the same blood draw sample and/or a marked peak aminotransferase (ALT, and/or AST)

Proprietary confidential information.

© 2017 Boehringer Ingelheim International GmbH or one or more of its affiliated companies. All rights reserved.

This document may not - in full or in part - be passed on, reproduced, published or otherwise used without prior written permission.

elevations ≥ 10 fold ULN. Patients showing these lab abnormalities need to be followed up according to [APPENDIX 10.2](#) of this clinical trial protocol and according to the "DILI checklist" provided in the ISF

2. For patients with abnormal liver function at baseline an elevation of AST and/or ALT ≥ 5 fold ULN combined with an elevation of bilirubin ≥ 2 fold ULN measured in the same blood draw sample. Patients showing these lab abnormalities need to be followed up according to [APPENDIX 10.2](#) of this clinical trial protocol and according to the "DILI checklist" provided in the ISF.

Although rare, drug-induced liver injury is under constant surveillance by sponsors and regulators and is considered a protocol-specified AESI. Timely detection, evaluation, and follow-up of laboratory alterations of selected liver laboratory parameters to distinguish an effect of the underlying malignancy on liver function from other causes are important for patient safety.

- *Dose limiting toxicity.* The definition of DLT is given in [Section 4.1.4.1](#)

Protocol-specified AESIs need to be reported to the Sponsor's Pharmacovigilance Department within the same timeframe that applies to SAE, see [Section 5.2.2.2](#).

If the investigator determines any protocol-specific AESI is related to study drug, the administration of the study drug must be managed according to [Section 4.1.4.3](#) of the protocol.

Expected Adverse Events

For expected (listed) AEs of afatinib, see the current version of the IB ([c01802941](#)).

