4.1.4.3 Dose reduction of afatinib

Treatment related toxicities will be managed by treatment interruptions and subsequent dose reductions of afatinib according to the schedule described in [Table 4.1.4.3: 1](#). Dose reductions will apply to individual patients only. Once the treatment dose has been reduced, it cannot be increased later.

To prevent the development of more severe adverse events, treatment related diarrhoea, nausea and vomiting or rash should be managed early and proactively as described in [Section 4.2](#).

Proprietary confidential information.

© 2017 Boehringer Ingelheim International GmbH or one or more of its affiliated companies. All rights reserved.

This document may not - in full or in part - be passed on, reproduced, published or otherwise used without prior written permission.

Table 4.1.4.3:1 Dose reduction scheme for afatinib

AE type and CTCAE Grade	Action	Dose reduction scheme

Events related to study drug:
 
 • Diarrhoea Grade 2 persisting for 7 or more consecutive days despite adequate anti-diarrhoeal medication/hydration • Reduced renal function to \geq Grade 2 as measured by serum creatinine, proteinuria or decrease in glomerular filtration rate of more than 50% from baseline • Any drug related AE Grade \geq3 	
Pause treatment until patient has recovered to Grade \leq1 or baseline¹.
 
Resume treatment at reduced dose according to schedule opposite.
 
If patient has not recovered to Grade \leq1 or baseline¹ within 14 days, study treatment must be permanently discontinued².
	
If patient was treated at dose level 3, resume treatment at dose level 2
 
If patient was treated at dose level 2, resume treatment at dose level 1
 
If patient was treated at dose level 1, resume treatment at dose level 0
 
If patient was treated at dose level 0, resume treatment at dose level -1
 
If patient was treated at dose level -1, discontinue afatinib.

Acute onset and/or unexplained worsening of pulmonary symptoms (dyspnoea requiring supplementation of oxygen with cough and/or fever)
	
Pause afatinib while clinical assessment to exclude ILD is completed.
	
If ILD is ruled out as a cause of symptoms, grade symptoms and relatedness and report as AEs. If AEs are not related, resume afatinib at current dose.
 
If ILD is confirmed, discontinue afatinib.

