
Acute onset of symptoms indicative of keratitis
	
Pause afatinib while clinical assessment of keratitis is ongoing.
	
If a diagnosis of ulcerative keratitis is confirmed, treatment with afatinib should be discontinued. Unless the treatment benefit for the patient outweighs the risks of worsening keratitis (blindness) in the opinion of the investigator.

Acute onset of symptoms indicative of cardiac failure and/or CTCAE Grade \geq 2 LVEF decrease and/or \geq20% decrease of LVEF from baseline
	
Pause afatinib while clinical assessment is ongoing and until patient recovers to Grade \leq1 or baseline¹
	
If patient has not recovered despite appropriate treatment to Grade \leq1 or baseline¹ within 14 days, study treatment must be permanently discontinued²

1 Baseline is defined as the CTCAE Grade at the start of treatment

2 In the event that the patient is deriving obvious clinical benefit according to the investigator's judgement, further treatment with afatinib will be decided in agreement between the sponsor and the investigator.

In the event of any unrelated adverse events, the investigator may choose to interrupt the medication for up to 14 days, but no dose reduction should occur once treatment is resumed.

Proprietary confidential information.

© 2017 Boehringer Ingelheim International GmbH or one or more of its affiliated companies. All rights reserved.

This document may not - in full or in part - be passed on, reproduced, published or otherwise used without prior written permission.

If the medication is interrupted for more than 14 days, the decision to continue with afatinib will be made by the BI clinical monitor in agreement with the investigator.

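### Section 5.2.2.1 sends a related hepatic-injury AESI to the dose-reduction table, which has no hepatic-specific trigger, so read literally no pause is mandated if the event is graded below 3

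*Protocol*

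**What the plan says.** Protocol Section 5.2.2.1 makes hepatic injury one of two protocol-specified AESIs. With normal baseline liver function it is met by AST and/or ALT of at least 3x ULN together with bilirubin of at least 2x ULN, "measured in the same blood draw sample and/or a marked peak aminotransferase (ALT, and/or AST") of at least 10x ULN. With abnormal baseline liver function it needs at least 5x together with at least 2x. No CTCAE grade enters the definition. The section then directs dosing: "If the investigator determines any protocol-specific AESI is related to study drug, the administration of the study drug must be managed according to" Section 4.1.4.3.

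Section 4.1.4.3 manages related toxicity through Table 4.1.4.3:1. Its one general trigger is "Any drug related AE Grade" 3 or higher. Three organ-specific rows carry a pause of their own:

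- Pulmonary symptoms: "Pause afatinib while clinical assessment to exclude ILD is completed".
- Keratitis symptoms: "Pause afatinib while clinical assessment of keratitis is ongoing".
- Cardiac failure symptoms or LVEF decrease: "Pause afatinib while clinical assessment is ongoing and until patient recovers to Grade" 1 or baseline.

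Below the table, the text also covers events not caused by the drug: "In the event of any unrelated adverse events, the investigator may choose to interrupt the medication for up to 14 days".

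**The concern.** The AESI is defined by laboratory multiples and the table's general trigger by CTCAE grade, and nothing in the protocol links the two. A related liver event can therefore meet the protocol's own definition of hepatic injury, be sent by a mandatory sentence to the dosing table, and find no row there that applies.

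Section 2.3 names four rare toxicities for early detection: drug-induced liver injury, keratitis, left ventricular dysfunction and interstitial lung disease (ILD). The last three have a pause row and liver injury does not. Grade 3 is not a general floor for action either, since the table acts below it for renal function, LVEF and persistent diarrhoea.

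Patient safety is at stake. Section 1.2 reports hepatic failure, some of it fatal, in under 1% of afatinib-treated patients. Section 4.1.4 has daily dosing continue until progression or unacceptable toxicity, so under the literal reading a child could stay on drug during the liver work-up unless someone decides otherwise.

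**Working it through.** The plan gives no figure to reproduce. The check compares the AESI definition with every place in the protocol that could mandate a hold.

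**Step 1. Triggers in Table 4.1.4.3:1**

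| Trigger | Reaches a liver event? |
|---|---|
| Related Grade 2 diarrhoea for 7 or more days | No |
| Related renal decline, Grade 2 or higher | No |
| Any related AE, Grade 3 or higher | Yes, if so graded |
| Pulmonary symptoms | No |
| Keratitis symptoms | No |
| Cardiac failure symptoms or LVEF decrease | No |

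One of the six can apply, and none is hepatic-specific.

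**Step 2. Other protocol text**

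- Section 4.2.2 tells the investigator to pause where applicable and refers back to the same table.
- Table 4.1.4.1:2 (dose-limiting toxicities) also starts at Grade 3 for a liver event.
- Section 3.3.4.1, item 6, and the emergency procedures in Section 4.2.1 cover ILD, keratitis and cardiac events only.
- Appendix 10.2 sets out the liver work-up and retesting but gives no dosing action.

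**Step 3. Which hepatic AESIs can be graded below 3?**

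Section 5.2.2.1 grades by CTCAE v3.0, but neither document prints the liver limits. Let A be the lower limit of Grade 3 for ALT/AST and B that for bilirubin, both in multiples of ULN. Assume the event is graded by its laboratory values. The combined event then escapes the general trigger only if ALT/AST is below A and bilirubin is below B. For normal-baseline patients the uncovered band is:

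ALT/AST from 3 up to A, with bilirubin from 2 up to B.

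| Assumed A, B | Band without a mandated pause |
|---|---|
| A = 5, B = 3 | ALT/AST 3-5x with bilirubin 2-3x |
| A = 4, B = 2.5 | ALT/AST 3-4x with bilirubin 2-2.5x |
| A = 3 or B = 2 | At most the boundary value |
| A < 3 or B < 2 | None |

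The 10x limb reaches Grade 3 for any A below 10. The abnormal-baseline limb starts at 5x, so it leaves at most the boundary value at A = 5 and nothing for A below 5. Over the range shown, the gap is confined to the normal-baseline combined criterion.

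**The case against.** The strongest reply is that the cross-reference supplies its own trigger. On that reading Section 5.2.2.1 names the event (a related AESI), Section 4.1.4.3 supplies the pause and step-down, and the mandatory sentence keeps its force. The text permits this but does not compel it, because every action in the table is tied to a listed trigger. Two sites could reasonably act differently on the same event, so the wording needs settling under either reading.

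The second reply is that safeguards already exist, and that stands:

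- Appendix 10.2 requires evaluation within 48 hours with repeat ALT, AST and bilirubin, imaging within a further 48 hours if the values are confirmed, and retesting at least weekly.
- Section 5.2.2.2 requires reporting to the sponsor within 24 hours.
- Sections 2.3 and 3.1.1 provide for data monitoring committee oversight.
- Section 3.3.4.1 requires stopping once the investigator judges that continuing might be injurious.

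None of these mandates a hold at a liver threshold. They do rule out two stronger inferences. A reader might conclude that hepatic injury goes unmanaged or that a hold is not allowed; neither is so. A reader might also take the 28-day spacing of routine dose checks as the time before dosing is reconsidered; the 48-hour evaluation brings a clinician in far sooner.

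Third, the documents do not establish that the band has any content. That is correct: it depends on limits they do not print, and on the grade the investigator assigns to the combined event.

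**Conclusion.** The point holds in conditional form. Unless Section 5.2.2.1 is read as itself triggering the table's action, the protocol mandates no pause for a related hepatic AESI graded below 3. Over the limits examined, this can occur only under the normal-baseline combined criterion, and only if the CTCAE v3.0 Grade 3 limits lie above 3x for ALT/AST and above 2x for bilirubin.

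The documents give no frequency for this band. The under-1% figure is for hepatic failure, a different event. Up to 38 further patients are planned. The investigator site file, including its checklist for drug-induced liver injury, and the Investigator's Brochure are not available, so the finding covers the protocol text only.

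A reader might look for an effect on the analysis through SAP Table 6.2:1, category C3, which checks dose changes after an adverse event against the protocol. The documents do not support one: C3 excludes no patient from any analysis set. This is an inexpensive safety improvement and does not threaten the trial's results.

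**What to change.** Add a row to Table 4.1.4.3:1 triggered by the hepatic-injury AESI definition itself, so that it does not depend on CTCAE limits:

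- Pause afatinib pending the Appendix 10.2 work-up.
- If the event is not related, resume at the current dose, as the pulmonary row already does.
- If it is related, manage it as a related Grade 3 or higher event: resume one level lower after recovery to Grade 1 or less or baseline within 14 days, and otherwise discontinue. Footnote 2 still applies: where there is obvious clinical benefit, "further treatment with afatinib will be decided in agreement between the sponsor and the investigator".

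Cross-refer to the row from Appendix 10.2. The pause pending work-up is the essential part.

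The drafting cost is one row and one cross-reference in an amendment. The clinical cost is a few extra pauses, some for events that prove unrelated. For related events the cost is larger. Section 4.1.4.3 does not allow a reduced dose to be raised again, and only one level lies below the MTD. A patient at level 0 (18 mg/m2) would move permanently to level -1 (12 mg/m2), a cut of (18 - 12)/18 = 33%. A second related event, or failure to recover in time, would mean discontinuation, subject to footnote 2 in the case of non-recovery. These children have no effective conventional therapy, so the amendment should state this trade-off openly.
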